9.4.3 Analysis of the Secondary Endpoint(s)

- 1) The ordinal scale at Day 15 will be used to estimate a proportional odds model within different categories of the ordinal scale at baseline. The hypothesis test will perform a strata- adjusted test to evaluate whether the common odds ratio for treatment is equal to one. The distribution of severity results will be summarized by treatment arm as percentages. There will be efforts to minimize loss to follow-up. However, small amounts of missing data may occur. In such cases, outcomes may be imputed based on rules described in the SAP. Sensitivity analyses will evaluate the impact of making different assumptions about missing observations. These analyses will be defined in the SAP.
- 2) Differences in time-to-event endpoints (e.g., time to recovery or time to at least a one category improvement in ordinal scale, time to death) by treatment will be summarized with Kaplan-Meier curves and 95% confidence bounds, using the Fine-Gray approach for competing events when appropriate.
- 3) Analysis of mortality data will be evaluated using a Cox proportional hazards model.

4) Desirability of outcomes response (DOOR). A revised ordinal scale has been constructed to incorporate SAEs. SAE may be related or unrelated to study product. Any SAE occurring after study product administration through Day 15 (or through Day 29) will be counted:

| |
|---|
| 1- Recovered (OS 1,2,3) |
| 2- Improved by at least 1 OS from baseline & no SAE |
| 3- Improved by at least 1 OS from baseline & SAE |
| 4- No change in OS from baseline & no SAE |
| 5- No change in OS from baseline & SAE |
| 6- Worsened by at least 1 OS from baseline |
| 7- Death (OS 8) |

*OS = ordinal scale score based on the 8-point scale

This DOOR scale will be evaluated at Day 15 and Day 29, and between arm differences will be tested using a Mann-Whitney U-statistic.

5) Change from baseline in ordinal scale at specific time points will be summarized by proportions (e.g., proportion who have a 1-, 2-, 3-, or 4-point improvement or 1-, 2-, or 3-point worsening).

6) Duration of event (e.g., duration of mechanical ventilation) will be summarized according to median days with quartiles and mean with SD.

7) Binary data (e.g., incidence of new oxygen use) will be summarized as a percent with 95% confidence intervals. Comparisons between arms will be presented as differences in proportions with 95% confidence intervals.

8) Categorical data (e.g., 28-day mortality or ordinal scale by day) may be summarized according to proportions by category and/or odds ratios with confidence intervals.

Procedures for handling missing data, including informative censoring (e.g., a missing duration of oxygen use endpoint due to a death), will be described in the SAP.

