6. STUDY PRODUCT

6.1 Study Product(s) and Administration

Subjects will be randomized into one of two arms (1:1).

| Arm 1 | Arm 2 |
|---------------------------------------|---|
| Baricitinib tablets + Placebo IV + | Placebo tablets + Dexamethasone IV + |

| | |
|---------------|---------------|
| Remdesivir IV | Remdesivir IV |
|---------------|---------------|

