6.3 Measures to Minimize Bias: Randomization and Blinding

6.3.1 Randomization

Randomization will be stratified by:

- Site
- Severity of illness at enrollment (by ordinal scale)
 - Hospitalized, on non-invasive ventilation or high flow oxygen devices, OR
 - Hospitalized, requiring supplemental oxygen

The randomization procedure will be described in the MOP.

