Appendix D - ACTT-4: Baricitinib/Remdesivir vs Dexamethasone/Remdesivir

differences between the ACTT-2 and RECOVERY studies as discussed above. In [Table 9](#), the first row of treatment effects is based on estimates from the ACTT-2 and RECOVERY results amongst the cohort that most closely resembles the ACTT-4 target population (those in ordinal 5 and 6). In the second row, the relative findings were changed to assume a gradual improvement in standard of care. This corresponds to a sample size of 1382 subjects. Sample size calculations were based on an exact unconditional score test of proportions using StatXact v11.1.0. Assuming 8% lost to follow-up, the sample size is planned to be approximately 1500 subjects.

The remaining lines demonstrate the power of the proposed sample size. There is good power of this trial for multiple scenarios unless the proportions surviving without invasive mechanical ventilation is much higher than anticipated (thought to be unlikely) or the difference in the proportions is smaller than anticipated (possible, but difficult to anticipate given the data available).

The formal analyses will be based on Kaplan-Meier estimates of the proportion of patients surviving without mechanical ventilation by Day 29 using a large sample normal approximation with Greenwood's variance formula. Accordingly, power for the final analysis is assumed to be equal or slightly higher than the power for the exact score as seen below.

Table 9: Sample size estimates and study power.

| | Total Sample Size | Proportion Dex Arm Surviving Through Day 29 Without Mechanical Ventilation | Proportion Bari Arm Surviving Through Day 29 Without Mechanical Ventilation | Power (unconditional exact score) | Power (KM + Greenwood) |
|--|-------------------|--|---|-----------------------------------|------------------------|
| - Baricitinib from ACTT-2 (OS 5 and 6) - Dexamethasone relative efficacy (only those on oxygen) from RECOVERY applied to ACTT-2 placebo arm | 1342 | 0.814 | 0.87 | 80.9% | 80.6% |
| Estimate of the above proportion applied to current outcomes given gradual improvement in care | 1382 | 0.85 | 0.9 | 80% | 80.5% |
| | | | | | |
| Other scenarios showing study power for the sample size of 1382 | 1382 | 0.9 | 0.95 | 94.5% | 94.9% |
| | 1382 | 0.9 | 0.925 | 37.0% | 37.5% |
| | 1382 | 0.85 | 0.925 | 99.4% | 99.4% |
| | 1382 | 0.8 | 0.875 | 96.6% | 96.6% |
| | 1382 | 0.8 | 0.85 | 68.2% | 68.9% |

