9.4 Statistical Analyses

9.4.1 General Approach

This is a double-blind, placebo controlled randomized trial testing a superiority hypothesis with a two-sided type I error rate of 5%. Secondary hypotheses have been ordered according to relative importance, with one key secondary hypothesis highlighted. These will be described according to the appropriate summary statistics (e.g., proportions for categorical data, means, medians for time-to-event data) and 95% confidence intervals.

A statistical analysis plan will be developed and filed with the study sponsor prior to unblinding of study and database lock.

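### Minor, free improvement: name the stratified (van Elteren) form of the Mann-Whitney test for DOOR in ACTT-4, since randomization is stratified by baseline ordinal score

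*Protocol*

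**What the plan says.** All references are to Protocol Appendix D (ACTT-4).

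- Section 9.4.3 item 4 builds a seven-level DOOR scale from the 8-point ordinal scale and serious adverse events, evaluates it at Day 15 and Day 29, and states that "between arm differences will be tested using a Mann-Whitney U-statistic". No strata are mentioned.
- The middle ranks (2 to 6) are relative to the patient's own baseline; rank 2, for example, is "Improved by at least 1 OS from baseline & no SAE". Rank 1 (recovered, ordinal 1 to 3) and rank 7 (death) are absolute.
- Item 1 of the same section specifies a strata-adjusted test "to evaluate whether the common odds ratio for treatment is equal to one" for the Day 15 ordinal scale.
- Section 6.3.1 stratifies randomization by site and by baseline severity: high-flow oxygen or non-invasive ventilation (ordinal 6) versus supplemental oxygen (ordinal 5). Allocation is 1:1 (section 6.1).
- Section 3 lists DOOR as an additional secondary endpoint. It is not among the five hypotheses of the fixed sequence in section 9.4.9.

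**The concern.** Stratified 1:1 allocation makes the arms nearly identical in their mix of ordinal 5 and 6. The ordinary Mann-Whitney variance ignores this: it is computed as if the mix could differ between arms by chance, so it includes rank variation between strata that cannot move the comparison. If baseline score predicts DOOR rank, the standard error is too large, the test rejects less often than its nominal level under the null, and power is lost.

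On the documents' own data baseline score is prognostic. Section 2.1.1 reports ACTT-2 median recovery of 5 versus 6 days in ordinal 5 and 10 versus 18 days in ordinal 6. Its Table 2 gives 28-day mortality of 1.9% and 4.7% against 7.4% and 12.9%. Recovery and death are absolute DOOR ranks, so this gap enters the pooled ranking directly.

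At stake are some sensitivity on a secondary endpoint and consistent handling of two outcomes derived from the same scale.

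**Working it through.** **The plan's own figure.** No power is stated for DOOR, so I checked the primary calculation that sets N. Section 9.2 says "This corresponds to a sample size of 1382 subjects", for 0.85 versus 0.90 at two-sided 5%. With 691 per arm:

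- pooled SE = √(2 × 0.875 × 0.125 / 691) = 0.01779; unpooled SE = √((0.1275 + 0.09) / 691) = 0.01774
- power (pooled) = Φ((0.05 − 1.96 × 0.01779) / 0.01774) = Φ(0.853) = 80.3%
- power (unpooled) = Φ(0.05 / 0.01774 − 1.96) = Φ(0.858) = 80.5%

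Table 9 states 80% and 80.5%, so this reproduces. N = 1382 is used below.

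**Inputs for DOOR.**

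- Stratum mix, from ACTT-2 in Table 2: ordinal 5, 287 + 276 = 563; ordinal 6, 104 + 113 = 217; 563/780 = 72%, leaving 28%.
- Recovery by Day 15 (assumption). With exponential recovery, 1 − 2^(−15/median) gives 88% and 82% for medians of 5 and 6 days, and 65% and 44% for 10 and 18 days (mean 54%). I take 82%/55% as the base case.
- Split over ranks 1 to 7 in the base case (assumption): ordinal 5, 82, 3, 1, 4, 1, 7, 2%; ordinal 6, 55, 16, 4, 8, 3, 9, 5%.

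**Formula.** Let R² be the share of mid-rank variance lying between strata. With balanced strata the true variance of the statistic is (1 − R²) times the variance the ordinary test uses, so

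true size = 2 × [1 − Φ(1.96 / √(1 − R²))].

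**Base case.** Mean relative mid-rank is 0.4651 in ordinal 5 and 0.5905 in ordinal 6, around an overall mean of 0.5.

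- Between-stratum variance = 0.722 × 0.0349² + 0.278 × 0.0905² = 0.00316
- Total mid-rank variance = 0.0488, so R² = 0.065
- 1.96 / √0.935 = 2.027, so true size = 0.043

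Power is compared at the common odds ratio that gives the van Elteren test 80%. A quick check is Φ(2.80 − 2.027) = 78%; the full calculation gives 77.8%.

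**Range**, all with a 72/28 mix and N = 1382:

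| Recovered, ordinal 5 / 6 | R² | True size, ordinary test | Power, ordinary | Power, van Elteren |
|---|---|---|---|---|
| 80% / 70% | 0.010 | 0.049 | 79.7% | 80% |
| 89% / 72% (Day 29 type) | 0.041 | 0.045 | 78.9% | 80% |
| 82% / 55% (base) | 0.065 | 0.043 | 77.8% | 80% |
| 85% / 40% | 0.186 | 0.030 | 72.4% | 80% |
| 85% / 30% | 0.266 | 0.022 | 67.2% | 80% |

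Simulation with 6,000 runs per row agreed: in the base case the ordinary test had size 0.0435, and across rows the van Elteren test had size 0.046 to 0.053. A separate simulation gave base-case sizes of about 0.038 (ordinary) and 0.049 (stratified) with a loss of about 2.5 points, and a loss of about 10 points at 85%/40%. Moving the ordinal-5 share between 60% and 80% changes the base case little (size 0.042 to 0.044, power 77.7% to 78.2%).

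**The case against.** **Silence is not a choice.** Item 4 neither says unstratified nor excludes a stratified form, and the protocol leaves statistical detail to a SAP that is not at hand. This stands as a limit: a reader might infer that an unstratified test has been prescribed, and the text does not establish that. But item 4 names a method rather than deferring it, and item 1 shows that the authors write strata into a test when they mean to.

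**The section is not uniformly stratified.** The Kaplan-Meier comparison in 9.4.2 and the Cox model in 9.4.3 item 3 name no strata either, and site is also a randomization factor. That is fair, and it is why this is an improvement and not a contradiction. The closest comparator is still item 1, which uses the same ordinal scale at the same day.

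**Baseline-relative scoring is not the cause.** It is tempting to say that the ranking mixes two scales, because ordinal 5 at Day 15 counts as unchanged for a baseline-5 patient and improved for a baseline-6 patient. That does not by itself cost power or invalidate the test, since both arms have the same expected mix. The loss depends on how strongly baseline predicts DOOR rank, here mainly through the absolute recovered rank. When that link is weak (80%/70%), almost nothing is lost.

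**Different target.** The pooled test addresses a win probability over the whole population; van Elteren compares within strata. Both are defensible. If the pooled quantity is preferred, keeping the pooled statistic but using its within-stratum variance recovers most of the loss: 79.9% power in the base case and 79.0% at 85%/40%.

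**Conclusion.** The point holds as a minor, free improvement. If item 4 means the ordinary Mann-Whitney test, that test is valid but mildly conservative: true size about 0.04 and a power loss of about 2 to 3 points under rates near the ACTT-2 medians. The loss is about 0.3 points at 80%/70%, about 8 to 10 at 85%/40% and about 13 at 85%/30%.

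The direction is secure whenever baseline score predicts DOOR rank. The size rests on assumed DOOR distributions, a proportional-odds treatment effect and the ACTT-2 mix as a proxy for ACTT-4.

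Two stronger readings are not supported. A reader might infer a false-positive problem, but the error runs the other way and type I error is not inflated. A reader might also infer that the DOOR and Day 15 results would conflict or that a confirmatory claim is weakened. The inconsistency is one of handling only; DOOR is not in the fixed sequence and the protocol claims no power for it.

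**What to change.** In section 9.4.3 item 4, and in the SAP, state that DOOR at Day 15 and at Day 29 is compared between arms with the stratified (van Elteren) Mann-Whitney test, stratified by baseline ordinal score 5 versus 6, and that the stratum-weighted DOOR probability is reported with its confidence interval. This brings item 4 into line with item 1 and with the severity factor used at randomization.

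The cost is one sentence. Section 8.1.1 already requires the ordinal score in order to randomize, so no additional data, patients or visits are needed. The wording should be settled before unblinding.

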9.4.4 Safety Analyses

Safety endpoints include death through Day 29, SAEs and Grade 3 and 4 AEs. These events will be analyzed univariately and as a composite endpoint. Time-to-event methods will be used for death and the composite endpoint. Each AE will be counted once for a given subject and graded by severity and relationship to COVID-19 or study intervention. AEs will be coded using the current version of the Medical Dictionary for Regulatory Activities (MedDRA). AEs will be presented by system organ class, duration (in days), start- and stop-date. Adverse events leading to premature discontinuation from the study intervention and serious AEs will be presented either in a table or a listing.

9.4.5 Baseline Descriptive Statistics

Baseline characteristics will be summarized by treatment arm. For continuous measures the mean and standard deviation will be summarized. Categorical variables will be described by the proportion in each category (with the corresponding sample size numbers).

9.4.6 Planned Interim and Early Analyses

A DSMB will monitor ongoing results to ensure subject well-being and safety as well as study integrity. The DSMB will be asked to recommend early termination or modification only when there is clear and substantial evidence of a treatment difference. More details about the interim analyses are described in [section 9.4.6.1](#) and [9.4.6.2](#) below as well as a separate guidance document for the DSMB.

9.4.6.1 Interim Safety Analyses

Safety analyses will evaluate Grade 3 and 4 AEs, SAEs, and all reportable VTE by treatment arm. Safety monitoring will be ongoing (see [section 8.3](#)). The unblinded statistical team will prepare these reports for review by the DSMB.

9.4.6.2 Interim Efficacy Review

The speed of recruitment impacts the utility of an interim analysis to inform reporting of results. If enrollment occurs rapidly, an interim efficacy analysis for a primary outcome that requires waiting until Day 29 to assess could be of limited use. A considerable portion of the sample could be enrolled during the waiting period to assess outcomes and clean data and the DSMB review may occur with only a small percentage of the final sample size remaining to be enrolled.

Therefore, the interim analysis for ACTT-4 will depend on the expected duration of enrollment. If full enrollment is expected within four months, no interim efficacy analyses are planned. This will be estimated by assessed by enrollment 1.5 months after first enrollment.

- If the study reaches or exceeds 1/3 of total enrollment within 1.5 months (assumes slightly slower enrollment at the beginning), no interim efficacy analysis will be performed.
- If the study does not reach 1/3 of total enrollment within 1.5 months, an interim analysis will occur after the first third of enrolled subjects have reached Day 29. The 28-day estimate will be based on a Kaplan-Meier estimator, which allows all subjects on-study to contribute data according to the amount of observation time contributed. The Lan-DeMets spending function analog of the O'Brien-Fleming boundaries will be used to monitor the primary endpoint as a guide for the DSMB with an overall two-sided type-I error rate of 0.05. Accordingly, the planned efficacy stopping boundaries are 3.7307 (33% information) and 1.9605 (100% information). Note that these values are approximate; the actual values will follow the prespecified error spending function and the information fractions determined by the analysis times.

9.4.7 Subgroup Analyses

Appendix D - ACTT-4: Baricitinib/Remdesivir vs Dexamethasone/Remdesivir

In addition to the planned subgroup analyses within each baseline ordinal scale, the following subgroup analyses for the primary outcomes are planned: geographic region, dexamethasone use prior to randomization, other steroid use prior to randomization, duration of symptoms prior to enrollment, age, race, sex and comorbidities. A forest plot will display confidence intervals across subgroups. Interaction tests will be conducted to determine whether the effect of treatment varies by subgroup.

9.4.8 Exploratory Analyses

An exploratory analysis will compare treatment efficacy estimates according to the various scales outlined in [section 8.1.2](#). Specifically, the probability of falling into category “i” or better will be compared between arms for each i.

[figure not shown]
Additional exploratory analyses will evaluate different scales for DOOR analyses that were described in 9.4.3 item 4.

9.4.9 Multiplicity Adjustment

A fixed sequence testing scheme will control the overall family-wise Type I error rate at a two-sided α level of 0.05. If the primary hypothesis is rejected at two-sided $\alpha < 0.05$, hypothesis testing will proceed to four key secondary endpoints. Hypothesis testing will follow the fixed ordering below (see figure):

- 1) Proportion not progressing to ordinal scale 7 or 8;
- 2) Day 15 clinical improvement on ordinal scale;
- 3) Proportion not progressing to ordinal scale 6, 7 or 8 (amongst baseline ordinal scale 5 only);
- 4) Overall mortality (Day 29); and
- 5) Time to recovery (Day 29).

Hypothesis testing will continue at the next endpoint with $\alpha = 0.05$ only if the previous hypothesis is rejected at $\alpha=0.05$. This method of carrying forward the α -level from the previous test is described in the FDA guidance on Multiple Endpoints in Clinical Trials [<https://www.fda.gov/regulatory-information/search-fda-guidance-documents/multiple-endpoints-clinical-trials-guidance-industry>].

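### The ACTT-4 fixed sequence does not hold the familywise error at two-sided 0.05 if the conditional 33% interim is run, because only the primary endpoint has interim boundaries

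*Protocol*

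**What the plan says.** Appendix D 9.4.9 makes an unqualified claim: "A fixed sequence testing scheme will control the overall family-wise Type I error rate at a two-sided" level of 0.05. Once the primary is rejected, "hypothesis testing will proceed to four key secondary endpoints", in a fixed order: Day 15 ordinal status, non-progression among baseline ordinal 5, mortality, and time to recovery. On the level it says "Hypothesis testing will continue at the next endpoint with" alpha of 0.05, provided the previous hypothesis was rejected at 0.05. The section does not mention an interim analysis.

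Appendix D 9.4.6.2 makes the interim conditional on the speed of enrollment. With fast enrollment, "no interim efficacy analysis will be performed". Otherwise: "If the study does not reach 1/3 of total enrollment within 1.5 months, an interim analysis will occur after the first third of enrolled subjects" (that is, once this third has completed Day 29). Lan-DeMets O'Brien-Fleming-type boundaries are then used "to monitor the primary endpoint as a guide for the DSMB with an overall two-sided type-I error rate of 0.05". The planned values are 3.7307 at 33% information and 1.9605 at 100%. No boundary or reduced level is given for any other endpoint.

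**The concern.** A fixed sequence at full alpha controls the familywise error when all hypotheses are tested at one analysis. With two looks, the primary can be rejected at either. Read literally, 9.4.9 then tests the next endpoint at 1.96 at whichever look that was. If a true-null secondary is positively correlated with the primary, an early crossing of the primary tends to coincide with a favourable interim value of the secondary. The look at which the secondary is tested is therefore partly chosen by the data.

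At the interim the primary needs a two-sided p of about 0.00019 (|Z| of 3.7307), while the next endpoint would need only 0.05 on about a third of the information (1382/3, roughly 460 subjects). After an early stop, a nominal p below 0.05 on Day 15 status could be reported as error-controlled when the stated control does not cover it.

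**Working it through.** **Inputs from the protocol.** Boundaries 3.7307 and 1.9605 at 33% and 100% information (9.4.6.2); 1382 subjects randomized 1:1, so 691 per arm; Table 9 rates (9.2); full 0.05 at each step (9.4.9).

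**Assumed.** The correlation rho between the primary and secondary statistics is not given, so it was varied from 0 to 1. Some positive correlation is expected, because death and invasive ventilation define the primary and are also the two worst Day 15 categories. The secondary is given the same 33% information fraction.

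**Step 1: reproduce the boundaries.** Per-tail spending at t = 0.33 is 2[1 − Φ(2.2414/√0.33)] = 0.0000955, which gives z = 3.7307. Solving the final boundary from the bivariate normal with correlation √0.33 gives 1.9605. Both match the protocol. (With t = 1/3 exactly, the values are 3.7103 and 1.9606.)

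**Step 2: drift and interim crossing.** Drift d = (p₂ − p₁)/√{[p₁(1 − p₁) + p₂(1 − p₂)]/691}. Interim crossing probability = 1 − Φ(3.7307 − d√0.33).
- 0.85 vs 0.90: d = 0.05/√[(0.1275 + 0.0900)/691] = 2.818, and the crossing probability is 1.7%. Recomputed power is 80.3%, against 80% in Table 9.
- 0.85 vs 0.925: d = 0.075/√[(0.1275 + 0.0694)/691] = 4.443, and the crossing probability is 11.9%.

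**Step 3: error for the first true-null secondary.** Simulation with 20 million draws (Monte Carlo standard error about 0.00005). The primary has drift d and the planned boundaries. The secondary is tested once at |Z| > 1.96, at the look where the primary is rejected. Two-sided error:

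| Table 9 rates | Drift | Interim crossing | rho 0.3 | 0.5 | 0.7 | 0.85 | 1.0 |
|---|---|---|---|---|---|---|---|
| 0.85 vs 0.90 (design) | 2.818 | 1.7% | 0.0384 | 0.0356 | 0.0327 | 0.0324 | 0.0378 |
| 0.90 vs 0.95 | 3.545 | 4.5% | 0.0464 | 0.0451 | 0.0433 | 0.0417 | 0.0415 |
| 0.80 vs 0.875 | 3.799 | 6.1% | 0.0482 | 0.0479 | 0.0473 | 0.0463 | 0.0399 |
| 0.85 vs 0.925 | 4.443 | 11.9% | 0.0508 | 0.0526 | 0.0547 | 0.0557 | 0.0540 |

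The largest value found was 0.0574, at drift 4.9 and rho 0.85.

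**Step 4: why the design effect shows no two-sided excess.** The gate itself leaves slack. With rho = 0 the error is 0.05 times the probability that the primary is rejected; at drift 2.84 that is 0.05 × 0.81 = 0.0405, as simulated. In the benefit tail alone, at the design effect, the error is 0.027, 0.029, 0.032 and 0.038 at rho 0.5, 0.7, 0.85 and 1.0, against 0.025.

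**Step 5: after the change.** With each secondary on its own 3.7307/1.9605 boundaries, the largest two-sided error in the runs was 0.045 (rho 0, drift 4). A secondary tested only at full information has a single look, so its error cannot exceed 0.05.

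**The case against.** The case for leaving the text alone has four parts.

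- **The interim may never happen.** It is run only if a third of enrollment is not reached in 1.5 months. Without it the claim in 9.4.9 is correct. This stands.
- **Interim testing of the secondaries is a reading.** Section 9.4.6.2 describes the boundaries as a guide for the DSMB on the primary, and no sentence says that secondaries are formally tested at that look. This stands as a caveat. But 9.4.9 opens the sequence whenever the primary is rejected, at a stated level and without exception.
- **The SAP may set secondary boundaries.** It is not shown, and such detail is normally left to it. Here, however, the protocol itself fixes the level, the gate and the claim of control, so secondary boundaries in the SAP would depart from 9.4.9 as written.
- **The size is small.** A reader might infer that the error exceeds its stated level at the planned effect, or that all four secondaries are inflated. The documents support neither. The protocol's standard is two-sided, and on that scale the design effect shows no excess; the per-tail figures use a 0.025 limit that the protocol does not state. Later endpoints are reached only through the earlier gates. With one intermediate gate (assumed drift 0.8 of the primary's, correlation 0.6), the error for the next null endpoint was 0.028 at the design effect, 0.048 at drift 4.44 and at most about 0.053 at drift 4.9.

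**Conclusion.** The claim in 9.4.9 is wrong as written for the case in which the interim is run. Strong control requires an error of at most 0.05 under every configuration, and a scenario that the sponsor tabulated exceeds it: 0.053 to 0.056 under 0.85 vs 0.925 at correlation 0.5 to 0.85. The maximum, about 0.057, lies at a drift slightly beyond that scenario. Of the four Table 9 scenarios simulated, only 0.85 vs 0.925 goes above 0.05. Weak control is not affected: if all nulls are true, any false claim needs a false rejection of the primary, which the spending function limits to 0.05.

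The result rests on an assumed correlation, on an equal information fraction for the secondary, and on applying the sequence at the interim as written. A larger figure, 0.088, is the limit if a secondary were tested at 1.96 at both looks; the protocol does not describe that, and it should not be read as the size of the problem.

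**What to change.** In 9.4.9, add a sentence along these lines: if the interim efficacy analysis is performed, each endpoint in the sequence is tested against its own Lan-DeMets O'Brien-Fleming-type boundary, computed at that endpoint's own information fraction (about 3.73 and 1.96 if that fraction is 33%). Day 15 and Day 29 endpoints accrue at different rates, so the fractions may differ. An equally valid alternative is to state that the secondaries are formally tested only at full information. Keep the full 0.05 for the single analysis when no interim is run, and carry the same rule into the SAP.

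The cost is one sentence. At the same information fraction the final threshold moves only from 1.960 to 1.9605, so power at the final analysis is essentially unchanged. The real downside is that secondary claims become unlikely if the trial stops at the interim.
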